4.4.2 Discontinuation Visit and Procedures

If participant is withdrawn from the study due to adverse effects, he/she will be treated as per routine recommended practice for the adverse event and will be scheduled to follow up in clinic. The frequency and interval of follow up will be depended on the clinical condition. If participant voluntarily withdrawal from the study, he/she will be followed up as per routine clinic schedule, which is once every 3 months.

5 TRIAL MATERIALS

The chlorhexidine impregnated sponge, named biopatch, is a protective disk (2.5 cm x 0.7 cm), which is hydrophilic polyurethane absorptive foam with chlorhexidine gluconate, in average of 86.8mg per disk.

5.1 Trial Product (s)

Refer to package insert in Appendix 2.

5.2 Storage and Drug Accountability

The product (biopatch) should be stored between 15C and 30C (59F and 86F), in the original packing. The expiratory date of product is indicated as year (4 digits) and month (2 digits). The product expires after the last day of the month indicated. The study material (biopatch) will be kept in the store room with temperature of 23 to 25 C, in peritoneal dialysis centre.

6 TREATMENT

6.1 Rationale for Selection of Dose

The biopatch disk (chlorhexidine impregnated sponge) comes with 3 sizes, (2.5 x 0.4cm; 92mg) (2.5 x 0.7cm; 52.5mg) (1.9 x 1.5 cm; 86.8mg). The outer diameter of the peritoneal dialysis catheter is 0.5cm, hence, the disk with larger diameter (2.5 x 0.7 cm with 86.8mg of chlorhexidine gluconate) will be used in the study.

6.2 Study Drug Formulations

The study material, which is chlorhexidine-impregnated sponge, comes with sterile package. Each package contains a single disk. The participants will be provided with sufficient number of packages to be used till the next clinic appointment.

6.3 Study Drug Administration

The skin around the catheter exit-site will be cleaned with 10% provodine iodine swabstick as per centre protocol, followed by drying the skin with sterile gauze. Then place the chlorhexidine-impregnated sponge (biopatch) around the catheter with blue printed side is facing upward and the white foam side, which releases the chlorhexidine gluconate, should be in contact with the skin.

6.4 Specific Restrictions / Requirements

Not applicable

6.5 Blinding

Not applicable

6.6 Concomitant therapy

Any topical cream used at the catheter exit-site will be documented.

7 SAFETY MEASUREMENTS

7.1 Definitions

An adverse event (AE) is any untoward medical occurrence in a patient or clinical investigation subject administered a pharmaceutical product and which does not necessarily have a causal relationship with this treatment.

A serious adverse event (SAE) or reaction is any untoward medical occurrence that at any dose:

- results in death
- is life-threatening
- requires inpatient hospitalisation or prolongation of existing hospitalisation
- results in persistent or significant disability/incapacity or
- is a congenital anomaly/birth defect
- is a medical event that may jeopardize the patient and may require medical or surgical intervention to prevent one of the outcomes listed above.

7.2 Collecting, Recording and Reporting of Adverse Events and Serious Adverse Events to CIRB

Reporting of adverse events involves the PI submitting to the approving CIRB the completed SAE Reporting Form within the stipulated timeframe. PI is responsible for informing the institution representative (local SAE resulting in death), sponsor or regulatory bodies as required and appropriate.

Reporting timeline to CIRB:

- SAE that result in death, regardless of causality, should be reported immediately - within 24 hours of the PI becoming aware of the event.
- Local life-threatening (unexpected/ expected) SAE should be reported no later than 7 calendar days after the Investigator is aware of the event, followed by a complete report within 8 additional calendar days.
- Local unexpected SAE that are related events, but not life-threatening, should be reported no later than 15 calendar days after the investigator is aware of the event.
- An increase in the rate of occurrence of local expected SAE, which is judged to be clinically important, should be reported within 15 calendar days after the PI is aware of the event.
- Local expected SAE should be reported annually (together with Study Status Report for annual review).
- Local unexpected and unlikely related SAE that are not life-threatening should also be reported annually (together with Study Status Report for annual review).
- Local unexpected AE that are related events should be reported at least annually (together with Study Status Report for annual review).
- Non-local unexpected SAE that are fatal or life threatening and definitely/probably/possibly related should be reported not later than 30 calendar days after the PI is aware of the event.

7.3 Safety Monitoring Plan

Patient's wellbeing and safety will be taken into considerations continuously during the trial period. If there is any contraindication observed during the interim of the study procedure that requires the discontinuation of the procedure, decision shall be made by the PI and Co-Investigators to discontinue the patient from the study.

7.4 Complaint Handling

Complaints will be handled by individual investigators who have direct contact with the patient and/ or have recruited the patient for the study.

Effort will be made by the PI or co-investigators in the study team to explain carefully the study procedure and visits to avoid any confusion.

8 DATA ANALYSIS

8.1 Data Quality Assurance

All measurements will be performed by experienced operators and the data quality will be assessed at the time of acquisition.

8.2 Data Entry and Storage

Electronic data will be stored in a secure database in the Department of Renal Medicine. The use of the data from the study will be controlled by the principal investigator.

9 SAMPLE SIZE AND STATISTICAL METHODS

9.1 Determination of Sample Size

This is just a pilot study only and hence there is no calculation of sample size and power.

9.2 Statistical and Analytical Plans

a. General Considerations

The primary outcome, which is exit-site infection rate, will be analysed using the Poisson regression and the secondary outcomes, time to first episodes of exit site infection, time to the episode peritonitis will be analysed by Cox regression and Kaplan Meier survival curve with log rank

b. Safety Analyses

The exit-site infection rate of the study cohort will be compared with the exit-site infection of historical cohort to examine any significant difference between two cohort in term of infection and adverse effects.

c. Interim Analyses

No interim analyses will be performed for this pilot study.

d. Describe the types of statistical interim analyses, including their timing.

NA

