2.3 Secondary Objectives

The secondary aim of the study is to examine the time to the first episode of exit-site infection, peritonitis rate, time to first episode of peritonitis, infection-related hospitalization, technique failure rate, mortality and adverse events and patient satisfaction with the use of chlorhexidine-impregnated sponge dressing

2.4 Potential Risks and Benefits:

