2.4.2 Potential Benefits

Chlorhexidine-impregnated sponge dressing can potentially be benefit for patients who are at high risk for exit site infection due to inability to clean the exit site daily including elderly, obese patients, patients with poor visual acuity etc. The use of weekly chlorhexidine-impregnated sponge dressing will also free patient from daily cleaning of exit site, which might provide extra-time for patients to enjoy other activities and potentially may improve the quality of life.

With the data collected from this pilot study, an adequately powered randomised controlled trial could be conducted to compare the effectiveness of once a week chlorhexidine-impregnated sponge dressing with daily topical anti-microbial cream in preventing exit site infection. If successful, our study has the potential to change current clinical practice and improve patient's outcomes.

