4.4 Discontinuation/Withdrawal

4.4.1 Discontinuation Criteria

The participant will be discontinued from the study if he or she develops adverse effects related to the use of chlorhexidine-impregnated sponge dressing, which includes local cutaneous skin reaction at exit-site, contact dermatitis at exit-site or developed exit-site infection.

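### Kaplan-Meier for time to first exit-site infection has no competing-risk handling for death and technique failure, so it modestly overstates one-year incidence

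*Combined protocol and SAP*

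**What the plan says.** Section 9.2 a (General Considerations) assigns the primary outcome, the ESI rate, to Poisson regression. It assigns the time-to-event secondary outcomes to Cox regression and a "Kaplan Meier survival curve with log rank". It does not say who is censored or when, and names no method for events that preclude the endpoint.

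Section 2.3 lists "technique failure rate, mortality and adverse events" among the secondary outcomes. Death and technique failure are therefore expected and recorded, but they have no stated role in the time-to-event analyses.

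Section 4.4.1 ends participation on "local cutaneous skin reaction at exit-site, contact dermatitis at exit-site or developed exit-site infection". Section 4.4.2 adds that a participant withdrawn for adverse effects "will be scheduled to follow up in clinic". Whether an ESI or peritonitis seen in that follow-up counts is not stated.

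Sections 3.1 and 4.3 give one cohort of 50 patients, each followed for one year. Section 1 notes that ESI can progress to peritonitis.

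**The concern.** Kaplan-Meier has no state for a patient who dies, or who stops peritoneal dialysis and loses the catheter. Such a patient can only be censored, and the estimator then gives that patient the future ESI risk of those still on dialysis. The complement of the curve estimates the ESI risk in a hypothetical population where nobody dies or has technique failure. It is not the share of patients who get an ESI within a year.

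At stake is the descriptive one-year risk on two secondary outcomes. For a pilot without a power calculation (section 9.1), usable estimates are the main product. Sampling error shows in the confidence interval, but this bias does not, because the interval is centred on a different quantity.

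**Working it through.** The documents state no event rate, competing-event rate or one-year risk, so there is no figure of the plan's own to reproduce. All rates below are assumptions. Only n=50 and the one-year horizon come from the protocol.

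**1. Size for first ESI.** Let pE be the true one-year incidence of ESI and pC that of death plus technique failure as first event, with constant hazards.

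- Total cumulative hazard: H = -ln(1 - pE - pC)
- ESI share: h = H × pE/(pE + pC)
- What Kaplan-Meier reports: 1-KM = 1 - exp(-h)

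| pE | pC | H | h | 1-KM | Excess (points) | Relative excess |
|---|---|---|---|---|---|---|
| 20% | 10% | 0.357 | 0.238 | 21.2% | 1.2 | 6% |
| 20% | 20% | 0.511 | 0.255 | 22.5% | 2.5 | 13% |
| 20% | 30% | 0.693 | 0.277 | 24.2% | 4.2 | 21% |

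For pE = 30% the relative excess is 6% to 23%.

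**2. Against sampling error.** The standard error at 20% and n=50 is √(0.2 × 0.8/50) = 5.7 points. An observed 10/50 has an exact 95% interval of 10.0% to 33.7%. On a second grid (ESI hazard λ of 0.1, 0.2 or 0.4 per year; competing hazard c of 0.1, 0.2 or 0.3), 1-KM = 1 - exp(-λ) and the cumulative incidence is λ/(λ+c) × (1 - exp(-(λ+c))). At λ = 0.2 these give 18.1% against 17.3%, 16.5% and 15.7%. Over the whole grid the excess is 0.5 to 4.2 points, against standard errors of 4.1 to 6.6, and stays below one standard error throughout.

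**3. The primary rate.** Events divided by person-time to exit return λ whatever the competing hazard. With 50 patients and λ = 0.2, c = 0.1 gives 8.64/43.20 = 0.20 per patient-year and c = 0.3 gives 7.87/39.35 = 0.20. A Cox model that censors competing events likewise estimates the cause-specific hazard without inflation.

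**4. Skin-reaction withdrawal.** This patient still has a catheter and can still get an ESI. Assume a withdrawal hazard of 0.05 to 0.2 per year, and an ESI hazard after withdrawal of r times the hazard before. Compared with the risk if follow-up continues, censoring at withdrawal gives no bias at r = 1. It is 0.2 to 3.9 points too low at r = 2 to 3, and 0.1 to 1.3 points too high at r = 0.5. The direction is unknown.

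**5. Peritonitis.** Section 4.4.1 also takes patients out at ESI. Assume hazards per year of 0.2 for peritonitis before ESI, 0.2 for ESI and 0.1 for death or technique failure, with the peritonitis hazard multiplied by r after ESI. If patients are censored at ESI, 1-KM is 1 - exp(-0.2) = 18.1%. The true incidence is 17.3% at r = 1, 19.8% at r = 3 and 22.6% at r = 6. Censoring at ESI can therefore outweigh the upward effect of censoring death and technique failure.

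**The case against.** The strongest defence is that the effect is small and peripheral. It touches a descriptive curve for secondary outcomes in a 50-patient pilot, lies within one standard error, and leaves the primary rate alone. The protocol also never says that death and technique failure are censored; that follows from the method named. Both observations stand. They limit the weight of the point but do not remove it, since the bias for ESI has a known direction and the remedy uses outcomes already listed.

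A reader might also infer three stronger claims that the documents do not support.

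- *The later trial would be too small.* Section 2.4.2 says that with the pilot data "an adequately powered randomised controlled trial could be conducted", comparing the dressing with daily antimicrobial cream. The pilot has only a dressing cohort, so its risk would describe the experimental arm. Overstating it narrows the expected difference from a higher control risk. With an assumed control risk of 40%, two-sided 5% and 80% power (pooled-variance formula for two proportions), n per arm is 82 for a dressing risk of 20%. It becomes 93, 110 and 137 for 21.2%, 22.5% and 24.2%, so the trial would be larger. Nor does the section say which pilot figure would be used.
- *The bias is always upward.* Working step 5 shows that it can run downward for peritonitis.
- *Skin-reaction withdrawal is another competing event.* The catheter remains at risk and clinic follow-up continues. Counting intolerance as competing would lower the reported ESI incidence and flatter the dressing.

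**Conclusion.** The point holds as a modest flaw in the analysis of secondary outcomes. With death and technique failure censored, one minus Kaplan-Meier overstates the one-year incidence of first ESI. The excess is 1.2 to 4.2 points for an assumed true 20% and assumed competing events of 10% to 30%.

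This rests on three assumptions: constant hazards, event rates that the documents do not give, and the reading that technique failure ends the catheter's exposure to ESI. For peritonitis no direction can be asserted, because the effect of discontinuation at ESI works the other way. The primary Poisson rate and any cause-specific Cox hazard stand as planned.

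**What to change.** Amend section 9.2 a as follows.

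- State the censoring rule for each time-to-event endpoint.
- Report Aalen-Johansen cumulative incidence for first ESI and first peritonitis, with death and technique failure as competing events.
- Label any Cox model cause-specific.
- Do not treat skin-reaction withdrawal as a competing event. Either count ESI and peritonitis recorded in the clinic follow-up that section 4.4.2 already provides, or label the estimate as on-dressing.
- Do not censor peritonitis at discontinuation for ESI. Count later peritonitis from clinic follow-up.

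The cost is SAP wording and standard software, plus carrying events from existing clinic follow-up into the dataset up to one year. The downside is one more quantity to explain, and an absolute risk that is no longer read directly off the Kaplan-Meier curve.

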1.2.3 Rationale for Study Population

Incident peritoneal dialysis (PD) patients will be recruited in the study. This is to prevent the cross over effect of topical antibiotics in the prevalent PD patients.

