3 STUDY POPULATION

3.1 List The Number and Nature of Subjects to be Enrolled.

Total of fifty incident peritoneal dialysis patients follow-up at Singapore General Hospital will be recruited for study.

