3.3 Inclusion Criteria

All adult incident peritoneal dialysis patients between 21 to 90 years old, who are followed up in Singapore General Hospital

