3.4 Exclusion Criteria

Patients with the following conditions will be excluded from the study

1. patients who have known history of allergy to chlorhexidine
2. patients who had previous history of peritoneal dialysis catheter exit-site infection
3. patients with mentally challenging conditions who are unable to give the valid consent for the study
4. patients who have been involved in the another study for exit site infection

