3.5 Subject Replacement

There will be no replacement for participants who dropout from study for various reasons.

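### Section 9.2b tests the study ESI rate for any significant difference from a historical cohort that is never defined; it should be a like-for-like rate ratio with a confidence interval, labelled descriptive.

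*Combined protocol and SAP*

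**What the plan says.** Section 9.2b, under Safety Analyses, states that "The exit-site infection rate of the study cohort will be compared with the exit-site infection of historical cohort", and gives the purpose as "to examine any significant difference between two cohort in term of infection and adverse effects". No test, significance level, effect measure or interval is named for this comparison. Section 9.2a names Poisson regression for the ESI rate as primary outcome, but does not mention the historical cohort.

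The study side is well described. Section 1.2.3: "Incident peritoneal dialysis (PD) patients will be recruited in the study". Section 3.3 admits "All adult incident peritoneal dialysis patients between 21 to 90 years old", and section 3.4 excludes "patients who had previous history of peritoneal dialysis catheter exit-site infection". Section 4.4.1 discontinues a participant who develops an ESI.

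On size, section 3.1 plans "Total of fifty incident peritoneal dialysis patients", section 4.3 follows each for one year, and section 3.5 adds: "There will be no replacement for participants who dropout from study for various reasons". Section 9.1 says that, because this is a pilot, "there is no calculation of sample size and power".

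**The concern.** Section 9.2b is the only place where the study ESI rate is set against an external reference. The hypothesis in section 2.1 is that the dressing is safe and effective, and section 2.4.2 expects the pilot to support a randomised trial, so readers will look to this comparison.

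Two things weaken it. First, nothing makes the cohorts comparable. The analyst could follow 9.2b to the letter and set a first-ESI rate in selected incident patients against an all-episode rate in unselected patients under whatever regimen was then in use. Second, the stated output is whether a difference is significant. With so few events that answer says little in either direction; an estimate with its interval would say what the data do and do not exclude.

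**Working it through.** **Step 1. The two sides of the comparison.**

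| Feature | Study cohort | Historical cohort |
|---|---|---|
| PD status | Incident only (1.2.3, 3.3) | Not stated |
| Age | 21 to 90 (3.3) | Not stated |
| Previous ESI | Excluded (3.4) | Not stated |
| ESIs counted per patient | At most one on study, since ESI ends participation (4.4.1) | Not stated |
| Follow-up | At most one year (4.3) | Not stated |
| How ESI is looked for | Investigator examination at six scheduled visits (4.3) | Not stated |
| Exit-site regimen | Weekly dressing after povidone-iodine cleaning (4.3.2, 6.3) | Not stated; mupirocin was used before 2013 and then withdrawn (section 1) |

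Each gap can move the historical rate. Prevalent patients or patients with a previous ESI may carry a different risk. First-ESI and all-episode rates agree only if every patient has the same constant risk that an earlier infection does not alter. The calendar period decides which regimen is the comparator. The documents give no basis for the direction or size of the net effect.

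**Step 2. Study exposure.** The ceiling is 50 × 1 = 50 patient-years. If follow-up ends at first ESI, the rate λ is constant and there is no other loss, exposure is T = 50 × (1 − e^(−λ))/λ, with λT expected ESIs. The documents give no λ, so it is assumed:

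- λ = 0.1: T = 47.6, 4.8 ESIs
- λ = 0.3: T = 50 × (1 − 0.7408)/0.3 = 43.2, 13.0 ESIs
- λ = 0.4: T = 41.2, 16.5 ESIs

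**Step 3. Interval when the observed rates are equal.** Assume λ = 0.3 and 200 historical patient-years, so 0.3 × 200 = 60 historical ESIs. Rate ratio = (13/43.2)/(60/200) = 0.301/0.300 = 1.00.

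- Wald: SE of the log ratio = √(1/13 + 1/60) = 0.306; exp(±1.96 × 0.306) gives 0.55 to 1.82.
- Exact: Clopper-Pearson limits for 13 of 73, converted to odds and multiplied by 200/43.2, give 0.51 to 1.85.

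The most favourable case is a historical rate known without error and the full 50 patient-years. The upper limit at equal observed rates is then 2.33, 1.84, 1.65 and 1.54 for λ = 0.1, 0.2, 0.3 and 0.4.

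**Step 4. Power.** There is no figure in the plan to reproduce. Two-sided 5% is assumed. Simulation: 50 patients, exponential time to first ESI, one year, Poisson historical count.

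- Mid case (0.3 per patient-year, 200 patient-years, no dropout), 1.5-fold increase: about 28% with the exact conditional test, about 35% with a Poisson Wald test.
- Same case with 20% dropout per year: about 25% (exact).
- Same case, no dropout, true doubling: about 72% (exact).
- 1.5-fold increase over historical rates of 0.15 to 0.5, 100 to 500 historical patient-years and 0% or 20% dropout: 12% to 44% (exact). With the Wald test the most favourable corner (0.5, 500, no dropout) reaches about 51%.

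**Step 5. Adverse events in the study cohort alone.** Exact 95% limits: for 0 of 50 the upper limit is 1 − 0.025^(1/50) = 7.1%; for 3 of 50 (6.0%) they are 1.3% to 16.5%.

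**The case against.** The best defence is that this is a declared pilot whose primary objective (section 2.2) is the rate in a single cohort, which does not depend on 9.2b. Section 9.1 openly gives no power calculation. Poisson regression, named in 9.2a, would ordinarily produce a rate ratio and interval if applied to this comparison. All of that stands. It excuses the low power and makes the missing interval a matter of wording. It does not supply a definition of the comparator, and low precision is the reason to report an interval instead of a verdict.

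Some stronger readings are tempting but not supported:

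- *That the plan will take a non-significant result as proof of safety.* Section 9.2b contains no such rule.
- *That a 1.5-fold increase is always more likely to be missed than found.* This depends on the assumed rate, the historical person-time and the test; the most favourable corner in step 4 reaches about 51%. A doubling is often detectable.
- *That a historical cohort could not have the adverse effects to be compared.* Section 4.4.1 names exit-site skin reaction and contact dermatitis. These could also arise from the povidone-iodine cleaning in section 6.3 or from topical creams (sections 1 and 6.6), and section 7.1 defines adverse events without requiring causality. The comparison is undefined, not impossible.
- *That the mismatch favours the dressing.* No direction can be established.

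**Conclusion.** The concern holds in this form: the comparator in 9.2b is undefined, the study cohort has features that an unspecified historical cohort need not share, and a search for significance is the wrong output for the information available. The first two parts come straight from the text and need no assumed figure.

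The third is illustrated only. Under the mid-case assumptions, identical observed rates would leave anything from about half to about 1.85 times the historical rate compatible with the data. Other assumed rates change the width; in the most favourable case of step 3 the upper limit still lies between 1.54 and 2.33. The documents give no historical rate, person-time, dropout rate or threshold for a material increase, so no single figure should be read as the plan's own.

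The change should be made before the historical data are examined. The primary objective stands without it, but 9.2b as written cannot be interpreted.

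**What to change.** Rewrite 9.2b as follows.

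1. **Cohort.** Consecutive incident PD patients of the same centre, aged 21 to 90, without previous ESI, from one calendar period and one exit-site regimen, both fixed in writing before the historical data are examined.
2. **Counting.** First ESI only in both cohorts, by the same written ESI criteria. Person-time ends at first ESI, end of PD, death, loss to follow-up or withdrawal, and is limited to one year in both.
3. **Output.** A Poisson rate ratio with 95% CI, labelled descriptive, with baseline characteristics side by side, including time since catheter insertion at entry. State that a non-significant difference will not be taken as evidence of safety.
4. **Adverse events.** Incidence in the study cohort with exact 95% CI. Any historical comparison is descriptive and limited to events recorded in both cohorts.
5. **Fallback.** If only an aggregate historical rate exists, report it beside the study rate with both intervals and call the comparison unadjusted and not like-for-like.

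With roughly 5 to 20 ESIs expected under the assumed rates, finer stratification or covariate adjustment is not advisable.

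The cost is SAP wording and some abstraction of historical records, whose availability the documents do not state. A restricted historical cohort will be smaller and the interval wider. Two limitations remain and should be stated: ESI may have been looked for less or more closely in the past, and only the study cohort is censored at dressing-related withdrawal.

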2 HYPOTHESIS AND OBJECTIVES

2.1 Hypothesis

We hypothesize that the use of weekly chlorhexidine-impregnated sponge dressing at the catheter exit site is safe and effective in the prevention of exit site infection in incident peritoneal dialysis patients

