2.4.1 Potential Risks

The common reported risk with use of chlorhexidine-impregnated sponge dressing is local skin irritation or contact dermatitis. The rare adverse event includes severe contact dermatitis which required removing the dialysis catheter, generalised allergic reactions and anaphylactic shock.

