4.3 Study Visits and Procedures

The participant will be followed up at 2, 6, 12, 24, 36 and 52 weeks of study and during each visit, the catheter exit-site will be examined by one of the investigators for any sign of infection or allergic reaction, and questionnaires about satisfaction with use of study material (biopatch) will be asked by a study team member at the 12 week of study. Each participant will be followed up for one year. After one-year of study period, there will not be additional follow-up for study purpose, however, participants will be continued followed up in SGH as per routine PD patients' schedule.

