Appendix 2: Package Insert

Instructions For Use EN (Please Read Carefully Before Using)

Product Description

BIOPATCH® Protective Disk with CHG is a hydrophilic polyurethane absorptive foam with Chlorhexidine Gluconate (CHG). The foam material absorbs up to eight times its own weight in fluid, while the CHG incorporated into the dressing inhibits bacterial growth under the dressing.

Chlorhexidine Gluconate is a well-known antiseptic agent with broad-spectrum antimicrobial and antifungal activity.

Indication For Use

BIOPATCH® containing Chlorhexidine Gluconate is intended for use as a hydrophilic wound dressing that is used to absorb exudate and to cover a wound caused by the use of vascular and non-vascular percutaneous medical devices such as: IV catheters, central venous lines, arterial catheters, dialysis catheters, peripherally inserted coronary catheters, mid-line catheters, drains, chest tubes, externally placed orthopedic pins, and epidural catheters. It is also intended to reduce local infections, catheter-related blood stream infections (CRBSI), and skin colonization of microorganisms commonly related to CRBSI, in patients with central venous or arterial catheters.

Precautions
BIOPATCH® should not be placed over infected wounds. It is not intended to be used as a treatment of percutaneous device-related infections.

Warnings

WARNING: DO NOT USE BIOPATCH® ON PREMATURE INFANTS. USE OF THIS PRODUCT ON PREMATURE INFANTS HAS RESULTED IN HYPERSENSITIVITY REACTIONS AND NECROSIS OF THE SKIN.
DO NOT RESTERILIZE/REUSE. REUSE OF THIS DEVICE (OR PORTIONS OF THIS DEVICE) MAY CREATE A RISK OF PRODUCT DEGRADATION AND CROSS-CONTAMINATION, WHICH MAY LEAD TO INFECTION OR TRANSMISSION OF BLOOD-BORNE PATHOGENS TO PATIENTS AND USERS.
FOR EXTERNAL USE ONLY. DO NOT ALLOW THIS PRODUCT TO CONTACT THE EYES, EARS, MOUTH, OR MUCOUS MEMBRANES.

THE SAFETY AND EFFECTIVENESS OF BIOPATCH® HAS NOT BEEN ESTABLISHED IN CHILDREN UNDER 16 YEARS OF AGE.

DO NOT USE BIOPATCH® DIRECTLY OVER BURN INJURY OR ON PATIENTS WITH A KNOWN

SENSITIVITY TO CHLORHEXIDINE GLUCONATE.

ADVERSE REACTIONS TO CHLORHEXIDINE GLUCONATE SUCH AS DERMATITIS, HYPERSENSITIVITY, AND GENERALIZED ALLERGIC

REACTIONS ARE VERY RARE, BUT IF ANY SUCH

REACTIONS OCCUR, DISCONTINUE USE OF THE

DRESSING IMMEDIATELY.

HYPERSENSITIVITY REACTIONS ASSOCIATED

WITH THE TOPICAL USE OF CHLORHEXIDINE GLUCONATE HAVE BEEN REPORTED IN SEVERAL

COUNTRIES. THE MOST SERIOUS REACTIONS

[INCLUDING ANAPHYLAXIS] HAVE OCCURRED IN

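### Section 9.2b names adverse effects as an aim but gives no way to measure them; the quantity it compares, the exit-site infection rate, cannot estimate skin or allergic reactions

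*Combined protocol and SAP*

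**What the plan says.** The hypothesis (section 2.1) is that the weekly dressing "is safe and effective in the prevention of exit site infection in incident peritoneal dialysis patients". The secondary objectives (2.3) end with "mortality and adverse events and patient satisfaction with the use of chlorhexidine-impregnated sponge dressing". On harms, section 2.4.1 states: "The common reported risk with use of chlorhexidine-impregnated sponge dressing is local skin irritation or contact dermatitis". It adds, as rare events, dermatitis severe enough to cost the patient the catheter, generalised allergy and anaphylaxis.

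The analysis text is short. Section 9.2a assigns Poisson regression to the exit-site infection rate and then says that "the secondary outcomes, time to first episodes of exit site infection, time to the episode peritonitis will be analysed by Cox regression", with Kaplan-Meier curves and a log-rank test. It gives no method for adverse events. Section 9.2b, headed as the safety analysis, has one sentence. Its subject is the exit-site infection rate, which is to be "compared with the exit-site infection of historical cohort to examine any significant difference between two cohort in term of infection and adverse effects". The historical cohort appears nowhere else: its size, period, exit-site care and adverse-event recording are not stated.

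Reactions are looked for in practice. At each of the six visits the exit site is examined "for any sign of infection or allergic reaction" (4.3), and 4.3.2 repeats this for adverse effects. Section 4.4.1 ends participation at a related reaction or at an exit-site infection.

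**The concern.** The variable that section 9.2b compares is also the primary outcome. It bears on one kind of harm, more infections than before. It carries no information on how many participants had a skin reaction, contact dermatitis or an allergic reaction, which are the harms that the protocol itself lists. Someone who followed section 9 exactly would finish with no estimate for the adverse-event objective.

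This matters more here than in a routine study. Section 1.2.1 says that the dressing has not been studied before for preventing exit-site infection in these patients, and section 2.4.2 says that the pilot is meant to lead to a randomised trial. A reaction frequency with an interval is one of the more useful results that such a pilot can hand on. Without a planned interval, a small or zero count could be reported as showing safety when the data remain compatible with an appreciable risk. A non-significant infection difference could be read in the same way.

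**Working it through.** The documents give no adverse-event rate and no calculation behind the sample size (9.1), so there is no figure to reproduce. The check has three parts.

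**1. What each part of the plan yields for adverse events**

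| Section | Content | Adverse-event estimate? |
|---|---|---|
| 9.2a | Infection rate; time to first exit-site infection; time to peritonitis | No |
| 9.2b | Infection rate against a historical cohort; adverse effects named as an aim | No variable, denominator or interval |
| 7.2 | Reporting to the review board, including a clinically important rise in expected SAEs | Oversight, not a study analysis |
| 7.3 | Decisions to discontinue individual participants | No |

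Section 9.2b can also be read generously, as comparing adverse effects with history as well. That reading needs a historical adverse-event frequency, and nothing says that one was recorded. If that cohort did not use the dressing (the documents do not say), it has no dressing-reaction rate to offer.

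**2. What a plain description would give**

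Inputs: n = 50 (section 3.1), all assumed to have at least one dressing applied; the counts x are illustrative. The exact (Clopper-Pearson) 95% limits are

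- lower = 2.5% quantile of Beta(x, n − x + 1), or 0 when x = 0;
- upper = 97.5% quantile of Beta(x + 1, n − x).

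For x = 0 the upper limit reduces to 1 − 0.025^(1/50) = 0.071.

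| Participants with the event | Percentage | Exact 95% CI |
|---|---|---|
| 0/50 | 0% | 0% to 7.1% |
| 2/50 | 4% | 0.5% to 13.7% |
| 5/50 | 10% | 3.3% to 21.8% |
| 10/50 | 20% | 10.0% to 33.7% |

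The chance of seeing at least one event is 1 − (1 − p)^50, where the true risks p are assumptions:

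| Assumed true risk | Chance of at least one in 50 |
|---|---|
| 10% | 99.5% |
| 5% | 92.3% |
| 1% | 39.5% |
| 0.1% | 4.9% |

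Common reactions would be seen and roughly estimated. Rare ones would probably be missed, and their absence would not exclude them.

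**3. Why a percentage alone is not enough**

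Planned follow-up is one year (4.3), so exposure cannot exceed 50 × 1 = 50 patient-years. Infection and related reactions cut it short (4.4.1), and dropouts are not replaced (3.5). Take 5 participants with a reaction. The percentage is 10% whatever the exposure. The rate is 5/50 = 0.10 per patient-year at the ceiling, but 5/25 = 0.20 if the average time on the dressing were six months (an assumption). The percentage cannot show that difference, so both should be reported.

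**The case against.** The best defence is that this is an uncontrolled pilot, that reactions are assessed at every visit, and that a count out of 50 leaves little room for analytic choice, so it could be tabulated later without much risk. Much of that stands. The primary outcome is unaffected and the gap can be repaired. But section 9.1 uses pilot status to justify the absence of a power calculation, not the absence of a safety summary. A descriptive table needs no power, and stating it now fixes the event categories and the denominator before results are seen.

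A reader might infer more than the documents support, in four ways.

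- **That section 9.2b says nothing about safety.** It names adverse effects as an aim, and an excess of infections on a new exit-site dressing would itself be a harm. Barring any safety reading of the infection comparison would go too far.
- **That section 2.4.1 and the package insert contradict each other.** The insert's warning, "ADVERSE REACTIONS TO CHLORHEXIDINE GLUCONATE SUCH AS DERMATITIS, HYPERSENSITIVITY, AND GENERALIZED ALLERGIC", continues "REACTIONS ARE VERY RARE, BUT IF ANY SUCH". Section 2.4.1 can be read as ranking the most often reported risk without stating a frequency, and it also calls the severe reactions rare. Any tension is limited to milder local reactions.
- **That adverse-event data are not being captured.** Section 11 mentions a monthly Excel sheet, but 12.2 refers to a data collection form and section 14 to CRFs and source records. Their contents are not given, so this needs checking and cannot be presumed a failure.
- **That there is no aggregate oversight.** Section 7.2 includes annual reporting and reporting of a rise in expected SAEs. That is oversight, though it does not estimate frequencies for the study report.

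**Conclusion.** The point holds, as a moderate gap in the prespecified analysis. Adverse effects are named as an aim in section 9.2b, but the plan supplies no measure of them, and the variable it does compare cannot estimate the non-infectious harms in section 2.4.1. The adverse-event objective and the corresponding part of the hypothesis are therefore left without an analysis.

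The size is best seen in what the study could say. With 50 participants, common local reactions can be estimated to within roughly ten percentage points either way, and zero events leave risks up to 7.1% compatible with the data. These figures assume that all 50 planned participants receive a dressing; fewer would widen the intervals. No documented reaction rate is available to refine them.

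**What to change.** Rewrite section 9.2b so that the main safety analysis is a within-cohort description in all participants who had at least one dressing applied:

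- Report number, percentage and exact (Clopper-Pearson) 95% CI for local skin reaction; contact dermatitis; generalised allergic reaction or anaphylaxis; SAEs; and discontinuation for an adverse effect.
- Add the rate of each per patient-time on the dressing, because of the early exits under 4.4.1.
- State that rare reactions cannot be excluded, citing the 7.1% upper limit for 0/50.
- Keep the historical infection comparison as exploratory, and do not treat a non-significant difference in it as evidence of safety.
- Compare adverse effects with history only if that cohort's adverse-event recording is described.

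The cost is one paragraph, one extra table, and a check that reaction type, SAEs, and the reason and date of stopping reach the study data; a few fields may need adding. The downside is a more modest safety statement. No visit or treatment procedure changes.
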